the DLRT. The DLRT may recommend on the administration of up to 2 additional infusions on D12 and D19 of a cycle for a future cohort based on rules described in [Section 10.3.2](#). The D5 infusion, and the D12/D19 infusions (if applicable) may be at the same dose as the preceding infusion or may be at a higher dose (= dose step). This will be based on tolerability of the lower dose level; occurrence of DLTs due to cytokine release syndrome, infusion related reactions or tumor lysis syndrome will trigger step dosing to evaluate MTD2. The DLRT may determine MTD3 based on the same rules. Starting with an initial lower dose / lower doses may improve tolerability of subsequently administered higher doses due to initial reduction of the bulk of blast cells, thereby improving efficacy. For a schematic overview of the different dose step options see [Figure 2](#). below. The term “dose level” administered to a cohort may therefore either refer to 2 – 4 infusions of the same dose (cohorts without a dose step) or to 2 – 4 infusions with up to 3 different doses (cohorts with 1 or more dose steps). In case of a dose step, the extended assessments for D1 and following apply also for D5/12/19 infusions (see [Schedule of Assessments, 7, Table 10](#)).

Figure 2. Example of Establishing Step Dosing Once MTD1 is Established in Schedule A

*The MTD1 will be determined by the DLRT

Administration of a prophylactic steroid dose (8 mg IV dexamethasone) within 1 hour prior to start of AMG 673 infusion on day 1 and day 5 and prior to each step-up dose of AMG 673, to mitigate cytokine release syndrome, is mandatory.

There is a ± 1 day window for dosing visits which may be implemented after discussion with the sponsor.

Intermediate dose level(s) may be evaluated as necessary based on DLRT recommendation after considering all information. For example, in the event that 1 subject experiences a dose limiting toxicity (DLT, see [section 6.2.1.3](#) for DLT definitions), the Dose Level Review Team (DLRT) will consider both the BLRM recommendation and all available data, including the nature and severity of the DLT. The DLRT will recommend the dose administered for the next cohort, which may be a dose lower than the next planned dose level.

Schedule B:

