6.2.1.3 Dose-cohort Study Escalation and Stopping Rules, Dose Limiting Toxicities (DLTs)

A DLT will be defined as any of the events described below occurring in a subject during the DLT window, unless clearly attributable to causes other than AMG 673. The DLT window for Schedule A will start on D1 (start of the administration of the first infusion) and last for 14 days for cohorts receiving 2 doses (ie, day 1 and day 5 dose) and for 28 days for subjects receiving 4 doses (ie, days 1,5,12,19). The DLT window for Schedule B will start on D1 (start of the administration of the first infusion) and last for the duration of cycle 1 and 2 (ie, 28 days). The CTCAE (version 4) will be used to assess will be used to assess toxicities/adverse events with the exception of CRS (see [Table 5](#) for grading of CRS).

DLT Evaluation

A subject is not DLT-evaluable if he/she drops out before completion of the DLT window for reasons other than an AE. All available safety data for subjects who are not DLT evaluable will still be evaluated and considered in DLRM recommendations. A subject will be DLT-evaluable if the subject has received the minimum cycle 1 doses planned for the respective cohort defined below:

- Schedule A : 2 doses with a 14-day DLT window, or 4 doses with 28-day DLT window
- Schedule B: completed $\geq 70\%$ of the planned target doses (eg, 10 doses out of a 14-day cycle 1 for cohort 1, at least 9 doses of the 12 planned at target dose cohort 2, etc) with 28-day DLT window

Exception: If a subject has completed treatment as planned but drops out of study before completing the DLT window due to progressive disease, they will still be considered DLT-evaluable and will not be replaced. The DLT window may also be extended retrospectively to assess events starting or persisting outside the window in case the DLT definition is time dependent (eg, in case of neutropenia, see below).

Any adverse event occurring outside the DLT window that is determined by the investigator to be possibly related to the investigational product, which is seen more frequently or is more severe than expected or is persistent despite appropriate

management, can be determined to be a DLT upon unanimous decision by the DLRT after review of the adverse event and all available safety data.

Events to be considered as DLTs and exceptions are listed below:

- Any treatment-related death

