- Grade 4 neutropenia persisting at 42 days after the last infusion in treatment cycle¹ in absence of evidence of active AML
- Grade 3–5 non-hematologic toxicity not clearly resulting from the underlying leukemia EXCEPT:
 - Alopecia
 - Grade 3 rash
 - Grade 3 fatigue, asthenia, fever, anorexia, or constipation
 - Grade 3 nausea, vomiting or diarrhea not requiring tube feeding, total parenteral nutrition, or requiring or prolonging hospitalization
 - Infection, bleeding, or other expected direct complication of cytopenias due to active underlying leukemia
 - Grade 3 infusion reaction, if successfully managed and resolves within 72 hours
 - Grade 3 tumor lysis syndrome if it is successfully managed clinically and resolves within 7 days without end-organ damage.
- Grade 3 or 4 isolated electrolyte lab abnormalities (ie, those occurring without clinical consequence) that resolve, with or without intervention, to < Grade 2 levels in < 72 hours will not be considered a DLT
- Grade 3 or 4 asymptomatic enzyme elevations including AST, ALT (without bilirubin elevation), GGT, lipase and amylase that resolve, with or without intervention, to ≤ Grade 2 within 7 days will not be considered a DLT.
- Grade 2 or 3 CRS meeting any of the criteria listed below:
 - Grade 2 CRS that does not resolve, with or without intervention to ≤ Grade 1 within 7 days will be considered a DLT
 - Grade 3 CRS that does not resolve, with or without intervention to ≤ Grade 2 within 5 days, or ≤ grade 1 within 7 days, will be considered a DLT
 - Grade 3 CRS reported at the initial dose (ie, at MTD₁; applicable only after MTD₁ has been defined) will be considered a DLT
 - Two separate grade 3 CRS events will be considered a DLT

Grade 4 CRS occurring during AMG 673 treatment.

See [section 6.2.1.3](#) and [6.2.1.4](#) for description of dose escalation and stopping rules and [section 3.4](#) for description of replacement of subjects.

Approved

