6.2.1.4 Dosage Adjustments, Delays, Rules for Withholding or Restarting, Permanent Discontinuation

Treatment Interruption

Significant events requiring a change in treatment will be managed by immediate treatment interruption.

Note: The definition of treatment interruption may include interruption of infusion or delay of the subsequent infusion.

Events leading to treatment interruption may include:

- The subject experiences a clinically relevant grade 4 adverse event related or not-related to IP
- The subject experiences a grade ≥ 3 CRS
- Technical problem with the infusion pump / syringe pump
- The investigational product is incorrectly prepared or administered (eg, overdose)

Treatment Interruption and Re-Start in Case of Logistical Issues

If the infusion interruption or the delay of the next infusion was up to 3 days, the next dose can be administered as planned. If the infusion interruption or the delay of the next infusion was > 3 days, the instructions for re-start after interruptions due to adverse events described below should be followed.

Treatment Interruption and Re-Start in Case of Adverse Events

Specific instructions apply in case of CRS: In case of grade 2 or 3 CRS, treatment must be interrupted and delayed until the event resolves to CRS grade ≤ 1 . The Amgen medical monitor has to be consulted prior to a planned re-start. In case of grade 4 CRS, treatment must be permanently discontinued. See [section 6.6](#) for further details.

For all other adverse events, the following instructions apply:

Any clinically relevant (as determined by the investigator) grade 4 adverse event related to IP should lead to an interruption of treatment. Treatment should be interrupted until the event has resolved to grade ≤ 1 . Treatment may be resumed at the same dose or a lower dose after the event is resolved to grade ≤ 1 (see below for guidelines). Drug interruptions are also allowed in case of SAE not related to IP per investigator's discretion.

Approved

Re-start at a lower dose level:

In the following cases, the next infusion administered should be at the previous (lower) dose level:

- If the event occurred during the infusion and caused an interruption of the infusion of >72 hours, or
- if the event is defined as DLT and the subject has derived clinical benefit in the opinion of the PI after consultation with the Sponsor

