In both cases, re-escalation to the target dose can be considered for the next infusion if treatment at the lower dose has been well tolerated. An intermediate dose level may be administered prior to stepping up to the target dose after consultation with the Amgen medical monitor. After the dose step, assessments of vital signs, pulse oximetry and clinical evaluation should be performed as per the schedule of assessments for D1, D2 and D3 (Table 6 for Schedule A or Table 12 for Schedule B).

Re-start at the same dose can be performed if the infusion was interrupted for < 72 hours or if the event occurred after the end of the infusion and did not cause a delay of the start of the next infusion \geq 72 hours.

In case of re-appearance of the same grade 4 adverse event, IP should be permanently discontinued.

For persistent or re-occurring clinically relevant grade 3 adverse event related to IP, a dose reduction should be considered.

In any case, restarting treatment after an interruption due to an adverse event should be performed under medical supervision. The following assessments should be performed as described in the Schedule of Assessments (Table 6 for Schedule A or Table 12 for Schedule B) for D1, D2, and D3: vital signs, pulse oximetry, and clinical evaluation. The subject should be hospitalized for at least 72 hours after re-start of the infusion.

If possible, the number of infusions at the target dose in a cycle should sum up to the planned number of infusions (ie, 2 or 4 for Schedule A or a minimum of 70% of the planned target doses for Schedule B). In this case, the subject would still be DLT-evaluable. However, if the next infusion could only be administered with a delay of 5 days, a new cycle should be started and the interrupted cycle would not be evaluable for DLT.

Permanent Discontinuation

A subject will permanently discontinue treatment with investigational product in the event of:

- Dose-limiting or other unmanageable toxicity. Exception: If a DLT occurs in a subject with a clear clinical benefit from treatment a restart at the same dose level, a lower dose and / or implementation of a dose step can be considered if the toxicity has resolved and after consultation with the sponsor
 - Grade 4 CRS.
 - Grade 2 or 3 CRS meeting any of the criteria listed below:
 - Grade 2 or 3 CRS that does not improve to \leq grade 1 within 7 days.
 - Grade 3 CRS that does not improve to \leq grade 2 within 5 days.

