- The Amgen medical monitor must be consulted prior to re-starting treatment
- If CRS occurred during AMG 673 infusion, infusion has been interrupted for at least 72 hours
- The event has resolved to grade ≤ 1 prior to re-starting treatment

AMG 673 therapy should be restarted 1 dose level below the dose at which the event occurred. If this lower dose level is well tolerated (ie, absence of grade ≥ 3 CRS), then a dose step up to the subject's target dose level can occur. An intermediate dose may be administered after consultation with the Amgen medical monitor prior to stepping up to the target dose.

Please also refer to the general guidance for re-start of treatment after adverse events in [Section 6.2.1.4](#)

For Grade 3 and 4 CRS, please see [Section 2](#) for DLT considerations.

Tumor Lysis Syndrome

Subjects with AML and WBC $<10,000/\text{mcl}$ or $10 \text{ cells} \times 10^9/\text{L}$ are considered to be at low risk for tumor lysis syndrome. WBC $>10,000/\text{mcl}$ and $<50,000/\text{mcl}$ are considered to be at intermediate risk, and subjects with WBC $>50,000/\text{mcl}$ are considered at high risk. This protocol requires that subjects have a maximum WBC count of $15,000/\text{mcl}$ or $15 \text{ cells} \times 10^9/\text{L}$.

Additional high-risk features include baseline uric acid $>450 \text{ mcg/L}$ (7.5 mg/dl), serum creatinine $> 1.4 \text{ mg/dL}$, and lactate dehydrogenase (LDH) greater than the ULN.

Patients with intermediate risk WBC count and elevated baseline uric acid ($> 450 \text{ mcg/L}$), serum creatinine $>1.4 \text{ mg/dl}$, or LDH greater than ULN will be recommended to receive allopurinol prophylaxis. Typical dosing is 600-800 mg/day administered BID or QID and should begin 3 days before the first dose of study drug. Patients should be well hydrated and supplemented with intravenous fluid as clinically indicated.

For grade 3 and 4 tumor lysis syndrome, please see [Section 6.2.1.3](#) for DLT considerations.

Infection Prophylaxis

Subjects who may experience neutropenia for 7 days or longer are at a high risk for infectious complications. As appropriate, these subjects should be administered prophylactic antibacterial (eg, fluoroquinolones), antifungal and antiviral medications. These subjects should be monitored for early signs of breakthrough infections after the initiation of antibacterial therapy to prompt additional evaluation and possible therapy modification.

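### The grade 3–5 non-hematologic DLT rule does not except CRS, so a first grade 3 CRS that resolves in time is a DLT as written, against the intent of the CRS criteria

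*Protocol*

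**What the plan says.** Protocol Section 6.2.1.3 opens with the rule "A DLT will be defined as any of the events described below occurring in a subject during the DLT window", subject to the event not being clearly due to something other than AMG 673. Meeting any one entry is therefore enough. Three kinds of entry matter here.

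- **General entry.** Grade 3–5 "non-hematologic toxicity not clearly resulting from the underlying leukemia EXCEPT" a list of seven exceptions. These include a grade 3 infusion reaction resolved within 72 hours and a grade 3 tumor lysis syndrome resolved within 7 days. CRS is not named.
- **Electrolyte and enzyme entries.** These stand outside that exception list but exclude events in so many words. The electrolyte entry ends "72 hours will not be considered a DLT".
- **CRS entries.** These state which CRS counts: grade 2 lasting beyond 7 days; grade 3 not at grade 2 or lower by day 5 or grade 1 or lower by day 7; grade 3 at the initial dose once MTD1 is defined; repeated grade 3, worded as "Two separate grade 3 CRS events will be considered a DLT"; and grade 4.

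SAP Section 5 takes the DLT from the investigator's answer on the Events eCRF, judged against this protocol section.

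**The concern.** The general entry and the CRS entries disagree on one class of event: a first grade 3 CRS, not at a defined MTD1 initial dose, that falls to grade 2 or lower within 5 days and grade 1 or lower within 7 days. The general entry counts it; the CRS entries do not. Grade 2, grade 4, prolonged, repeated and MTD1-dose CRS get the same answer either way.

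The classification matters in four places.

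- **Endpoint and model.** DLT incidence is part of the primary endpoint (Protocol 10.1.1) and is the BLRM input (10.4.2). CRS is the only identified risk in Table 1.
- **Step dosing.** In Schedule A, "occurrence of DLTs due to cytokine release syndrome, infusion related reactions or tumor lysis syndrome will trigger step dosing to evaluate MTD2" (Section 3.1). This trigger does not depend on the prior.
- **The subject.** Under Section 6.2.1.4 a DLT means permanent discontinuation, with an exception that begins "If a DLT occurs in a subject with a clear clinical benefit from treatment a restart at the same dose level". After a resolved grade 3 CRS, Section 6.6 instead says "AMG 673 therapy should be restarted 1 dose level below the dose at which the event occurred".
- **Labelling.** The protocol says infusion reactions may be impossible to tell from CRS. A resolved grade 3 infusion reaction is excepted and a resolved grade 3 CRS is not, so the name given to the event could decide the DLT call.

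**Working it through.** **1. The text**

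| Question | General entry | CRS entries |
|---|---|---|
| Does it cover a first, resolved grade 3 CRS? | Yes: grade 3, non-hematologic, not excepted | No criterion is met |
| Does it exclude anything? | Only the seven listed exceptions | No; the entries only add events |
| Is precedence stated? | No | No |

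The mention of CRS as an exception in the opening paragraph of 6.2.1.3 concerns the grading scale (Table 5 instead of CTCAE), not DLT status.

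Intent can be read from elsewhere. On the literal reading, the 5/7-day, MTD1 and two-event criteria for grade 3 CRS would do nothing. Section 6.2.1.4 says "Specific instructions apply in case of CRS" and repeats the same CRS criteria for discontinuation. Section 6.6 allows the next infusion after a resolved grade 3 CRS. The CRS entries are meant to govern.

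**2. The plan's own DLT figures**

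P(at least 1 DLT) = 1 − (1 − p)^n:

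- n = 3: 1 − 0.90³ = 0.271 and 1 − 0.67³ = 0.699, against the stated 27–70%.
- n = 4: 1 − 0.90⁴ = 0.344 and 1 − 0.67⁴ = 0.799, against the stated 34–80%.

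These reproduce and are not in dispute. The reading changes which p applies. The documents give no rate for this event, so assume 5–20% of subjects, none with another DLT. A 10% DLT rate under the CRS criteria becomes 15–30%, and P(at least 1 DLT) rises from 27% to 39–66% (n = 3) or from 34% to 48–76% (n = 4). A 20% rate becomes 25–40%, and passes the 0.33 upper limit of the target interval if the added rate is 15% (0.20 + 0.15 = 0.35).

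**3. Effect on the BLRM**

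Model (Protocol Appendix H): logit(p) = log a + b·log(d/d_ref), with P(p ≤ 0.05 at d_ref) = 0.05 and P(p ≤ 0.40 at the lowest dose) = 0.90. SAP Appendix C gives the simulation values: p = 0.30 at d_ref, and 0.05 at 72 µg (Schedule B) or 0.02 at 0.45 µg (Schedule A). These are taken here as prior medians. The d_ref and the prior correlation are not available and are varied.

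- sd(log a) = [logit(0.30) − logit(0.05)] / 1.645 = (−0.847 + 2.944) / 1.645 = 1.275.
- sd(log b), solved from the 0.90 condition at correlation 0 and −0.5: 1.84 and 0.76 (Schedule B); 2.55 and 1.18 (Schedule A).
- Model dose: highest P(0.20 < p ≤ 0.33) among doses with P(p > 0.33) < 0.25.
- Newly ruled out: the model dose is at or above the next planned level without the event and below it with the event.

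Schedule B, no DLT at 72 µg, 0 DLTs versus 1 at 110 µg. Model dose in µg, without → with the event:

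| Correlation, cohort size | d_ref 160 | d_ref 240 | d_ref 360 | d_ref 480 |
|---|---|---|---|---|
| 0, n = 4 | 110 → 110 | 160 → 160 | 240 → 160 | 360 → 240 |
| 0, n = 3 | 110 → 110 | 160 → 110 | 240 → 160 | 360 → 160 |
| −0.5, n = 4 | 160 → 110 | 240 → 160 | 360 → 160 | 480 → 240 |
| −0.5, n = 3 | 160 → 110 | 240 → 110 | 360 → 160 | 480 → 160 |

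The model dose falls in 13 of 16 cells. The next planned level, 160 µg, is newly ruled out in 4, with these values of P(p > 0.33) against the 0.25 limit:

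- 0.262 (correlation 0, d_ref 240, n = 3)
- 0.473 and 0.549 (correlation −0.5, d_ref 160, n = 4 and n = 3)
- 0.297 (correlation −0.5, d_ref 240, n = 3)

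If 72 µg already has 1 DLT in 4 on both readings, one reclassified event in 4 at 110 µg newly rules out 160 µg in 6 of 8 cells: 0.31–0.52 with the event, 0.10–0.23 without.

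Schedule A, no DLT from 0.45 to 36 µg, d_ref 72/110/160/240/360 µg, both correlations, n = 3 or 4 (20 cells): one reclassified event at 72 µg newly rules out 110 µg in 0 cells. Two events in different subjects do so in 7.

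**The case against.** The best reply is that the list has to be read as a whole and the specific rule displaces the general one. Section 6.2.1.3 says it lists both DLTs and exceptions. CRS has its own grading table, with grades 1 to 4 only. Grade 4 CRS has its own line, which would be redundant if the general entry covered CRS. The discontinuation list in 6.2.1.4 names the CRS events that end treatment, and a first, resolved grade 3 CRS is not one of them. All this is right and establishes the intent. It does not remove the literal rule. The same list shows how its authors exclude an event when they do so outside the exception list, and the CRS entries do not do that. A DLT definition applied at about 10 sites should not rest on inference. The Section 6.6 pointer for CRS DLTs does not help, since it sends the reader to Section 2.

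The second reply, that the harm is limited, largely stands. The error over-counts DLTs, so it leans toward lower doses and stopped treatment, not overdose. In 9 of the 13 Schedule B cells where the model dose falls, 160 µg is still allowed. The medical monitor must be consulted before restart, and the DLRT reviews all grade 3 or higher events (Section 10.3.2). That review is only a partial safeguard: under Section 3.1 the DLRT chooses at or below the model's dose, so it cannot undo a ceiling lowered by a wrong flag. Nothing in the documents shows that a flag has been misassigned.

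**Conclusion.** The concern holds. As written, the general entry makes a first, resolved grade 3 CRS a DLT, contrary to the CRS criteria in the same section and to Sections 6.2.1.4 and 6.6. The textual finding needs no assumption.

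The consequence is moderate. One such event can lower the model dose but seldom blocks the next planned step by itself; it does so more readily when another DLT is already on record. These figures depend on the assumed d_ref, prior correlation and cohort data, and the frequency of the event is unknown. The step-dosing trigger and the subject's discontinuation rule depend on the flag itself, whatever the prior. This should be fixed: it is a contradiction in a primary-endpoint definition, on the drug's one identified risk.

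**What to change.** Add one line to the exception list of the grade 3–5 non-hematologic entry in Section 6.2.1.3: *CRS, which is assessed only by the CRS criteria below*. Before the next BLRM run, re-check the DLT flags already entered for first, resolved grade 3 CRS. In the same edit, change the Section 6.6 cross-reference for grade 3 and 4 CRS from Section 2 to Section 6.2.1.3, where the tumor lysis pointer already goes.

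The cost is low: one line, one cross-reference and a limited check of existing records. The model and its decision thresholds do not change.

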9.2.2 Adverse Events

9.2.2.1 Reporting Procedures for Adverse Events That do not Meet Serious Criteria

The investigator is responsible for ensuring that all adverse events observed by the investigator or reported by the subject that occur after consent through the end of study are reported using the Event CRF.

The investigator must assign the following adverse event attributes:

- Adverse event diagnosis or syndrome(s), if known (if not known, signs or symptoms),
- Dates of onset and resolution (if resolved),
- Severity [and/or toxicity per protocol],
- Assessment of relatedness to investigational products, medical devices (syringe, infusion pump), or study procedure / activity
- Action taken.

The adverse event grading scale used will be the CTCAE, version 4.0. The grading scale used in this study is described in [Appendix A](#). **Exception:** CRS will be graded according to the guidelines provided in [Table 5](#) [based on the adopted grading system referenced in [Lee et al 2014](#)].

The investigator must assess whether the adverse event is possibly related to the investigational products, medical devices and/or study procedure / activity. This relationship is indicated by a “yes” or “no” response to the question: Is there a reasonable possibility that the event may have been caused by the investigational product, medical device, and/or study procedure / activity?

The investigator is responsible for reviewing laboratory test results and determining whether an abnormal value in an individual study subject represents a clinically significant change from the subject's baseline values. In general, abnormal laboratory findings without clinical significance (based on the Investigator's judgment) are not to be recorded as adverse events. However, laboratory value changes that require treatment or adjustment in current therapy are considered adverse events. Where applicable, clinical sequelae (not the laboratory abnormality) are to be recorded as the adverse event.

The investigator is expected to follow reported adverse events until stabilization or reversibility.

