Appendix G. Expected Disease-related Events by System Organ Class (SOC)

System Organ Class (SOC)	Disease-related Events
Blood and lymphatic system disorders	Febrile neutropenia, anaemia, neutropenia, thrombocytopenia, leukopenia, leukocytosis, disseminated intravascular coagulation
Cardiac disorders	Palpitations, tachycardia
Ear and labyrinth disorders	Ear pain, tinnitus
Eye disorders	Blurred vision, photophobia
Gastrointestinal disorders	Abdominal distention, abdominal pain, constipation, diarrhoea, gingival pain, nausea
General disorders and administration site conditions	Fatigue, pyrexia, malaise, pain, chest pain
Infections and infestations	Infections ¹ , sepsis
Investigations	Alanine aminotransferase increased, aspartate aminotransferase increased, alkaline phosphatase increased, white blood cell count decreased, haemoglobin decreased, platelet count decreased
Metabolism and nutrition disorders	Decreased appetite, hypokalaemia, hyponatraemia, hypomagnesaemia, hypophosphataemia, hypocalcaemia, hyperuricaemia
Musculoskeletal and connective tissue disorders	Skeletal pain, muscular pain, arthralgia, generalized muscle weakness, neck pain
Nervous system disorders	Cranial nerve disorder, dizziness, headache, lethargy, meningismus, syncope
Respiratory, thoracic and mediastinal disorders	Cough, dyspnea, epistaxis, pleuritic pain
Other	Haemorrhage ²

¹ Represents preferred terms under *Infections and infestations* SOC

² Represents haemorrhage HLGT preferred terms contained within multiple SOCs

Coded: MedDRA v17.0

Approved

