#### Dose Limiting Toxicities (DLT)

**DLT will be determined by “Is this event a Dose Limiting Toxicity (DLT)?” equal to “Yes” on the Events eCRF. Investigators will determine whether an adverse event qualifies as a DLT per protocol Section 6.2.1.3**

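### A persistent, symptom-free grade 3-4 laboratory abnormality can be a DLT, yet the recording rule lets it stay off the Events eCRF, the SAP's only source of DLTs

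*Protocol*

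**What the plan says.** **DLT criteria (Protocol 6.2.1.3).** The base rule makes a DLT of "Grade 3–5 non-hematologic toxicity not clearly resulting from the underlying leukemia EXCEPT" for a list of exceptions. Two further items concern laboratory values:

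- Electrolytes: the item covers "Grade 3 or 4 isolated electrolyte lab abnormalities (ie, those occurring without clinical consequence"). They are exempt if, treated or not, they drop below grade 2 before 72 hours have passed.
- Enzymes: "Grade 3 or 4 asymptomatic enzyme elevations including AST, ALT (without bilirubin elevation), GGT, lipase and amylase that resolve" to grade 2 or lower within 7 days are likewise not DLTs.

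The section opens by excluding events clearly attributable to something other than AMG 673.

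**Recording rule (Protocol 9.2.2.1).** "In general, abnormal laboratory findings without clinical significance", as judged by the investigator, "are not to be recorded as adverse events". Laboratory changes that need treatment, or a change to current therapy, are adverse events.

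**Source of the DLT count (SAP 5).** A DLT exists when the DLT question on the Events eCRF is answered yes, and "Investigators will determine whether an adverse event qualifies as a DLT per protocol Section 6.2.1.3". SAP 9.6.1 fits the BLRM to the subject incidence of those DLTs. SAP 9.6.3 provides laboratory listings, high/low flags and grade-shift tables. It derives no time to resolution and does not compare laboratory grades with the DLT flag.

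**The concern.** The DLT criteria reach values that cause no symptoms, while the recording rule filters out values judged not to matter clinically. A value that passes the first and is dropped by the second has no Events entry, so nobody is asked the DLT question about it. It is then missing from the primary endpoint and from the data behind the dose recommendation, although the laboratory database holds it.

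The loss runs in one direction: an unrecorded event can only lower the DLT count. Protocol 3.1 brings the BLRM into use for MTD estimation once a DLT is observed, so missing the first one would also delay the model.

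**Working it through.** **1. Is a persistent symptom-free value a DLT?** The two laboratory items state only when a value is not a DLT. A grade 3-4 electrolyte abnormality still at grade 2 or above at 72 hours, or an enzyme rise still above grade 2 after 7 days, fails the exemption. The base rule for grade 3-5 non-hematologic toxicity then applies, subject to attribution. This is an inference from two parts of one section, but without it the time limits would have no function.

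**2. Must it be recorded?** No section requires a laboratory value that meets a 6.2.1.3 criterion to be entered whatever its judged significance. What remains exposed is a value that is untreated, symptom-free, judged insignificant and leads to no change of therapy. Lipase and amylase are the clearest case, because the withholding rules in Protocol 6.4 do not name them.

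**3. Would the deciding date be on file?** Protocol 9.1.2 requires a decrease in severity to be recorded only for DLTs and for adverse events that interrupt or delay treatment. For any other recorded event, the date of falling to the exempting grade may be absent, although that date decides DLT status.

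**4. The plan's own figures.** The synopsis and SAP 3.2 give the chance of seeing at least one DLT at true rates of 10-33%. With P = 1 − (1 − p)^n:

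| n | p = 0.10 | p = 0.33 | Plan |
|---|---|---|---|
| 3 | 27.1% | 69.9% | 27-70% |
| 4 | 34.4% | 79.9% | 34-80% |

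They reproduce, and they presume complete capture. If a share u of true DLTs goes unrecorded, p becomes p(1 − u). The documents give no u, so these values are assumptions:

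| u | n = 3 | n = 4 |
|---|---|---|
| 10% | 25-65% | 31-76% |
| 25% | 21-57% | 27-68% |
| 50% | 14-42% | 19-51% |

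**5. Effect of one lost DLT, as illustration.** Protocol 3.1 requires a probability below 0.25 that the rate is in the excessive or unacceptable range, that is, above 0.33. The BLRM cannot be rebuilt because its full prior and reference dose are not shown. A single-dose beta-binomial model stands in: with prior Beta(c, c) and x DLTs in n subjects, the posterior is Beta(c + x, c + n − x).

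| Subjects | DLTs | P(rate > 0.33), uniform prior | P(rate > 0.33), Beta(0.5, 0.5) prior |
|---|---|---|---|
| 4 | 1 | 0.468 | 0.394 |
| 4 | 0 | 0.135 | 0.065 |
| 6 | 2 | 0.578 | 0.528 |
| 6 | 1 | 0.270 | 0.204 |

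The uniform-prior values at 4 subjects can be checked by hand: 0.67^5 = 0.135 for no DLT, and 0.135 + 5 × 0.33 × 0.67^4 = 0.468 for one.

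At 4 subjects, losing the only DLT crosses 0.25 under both priors. At 6 subjects, going from two DLTs to one crosses it under Beta(0.5, 0.5) but not under the uniform prior. The raw rate at 6 moves from 2/6 = 33.3%, just above the 0.20-0.33 target interval, to 1/6 = 16.7%, below it.

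**The case against.** Much of the loop is already closed.

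- The recording rule is worded as a general one and rests on judgment. Lack of clinical consequence is not lack of clinical significance, and many investigators would call a persistent grade 3-4 value significant. This stands, and it is why the frequency is unknown.
- Treated values are adverse events under 9.2.2.1 itself. A recognised DLT also leads to permanent discontinuation, or to sponsor consultation, under 6.2.1.4, which is a change of therapy. This stands for values someone has recognised as DLTs; it does not help with those nobody has.
- AST and ALT have their own route: withholding rules in 6.4.2, and close observation with CRF capture of potential liver injury in Appendix A. This stands, and it leaves AST and ALT much less exposed than lipase or amylase.
- In multiple-subject cohorts the investigator reviews laboratory data on day 7 and confirms DLT status in writing (Protocol 3.1). An enzyme rise that began after the first infusion cannot have exceeded a 7-day limit by then, and the interval for later subjects is 96 hours.
- The DLRT reviews laboratory data and grade 3 or higher toxicities that are not DLTs, and may dose below the model (Protocol 3.1 and 10.3.2). Data management looks for omissions (12.3). Both make silent loss less likely, but neither sets the eCRF flag.

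A reader might also infer that Appendix G widens the gap, since it lists "Alanine aminotransferase increased, aspartate aminotransferase increased" and several electrolyte changes as expected disease-related events. The documents do not support this. Protocol 9.1.1 and 9.2.1 put disease-related events on the Event CRF, and the SAP counts them among treatment-emergent events. Listing there does not mean absence from the Events data.

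**Conclusion.** The gap is real but narrow. It covers grade 3-4 electrolyte or enzyme abnormalities that outlast the exemption, are not clearly due to leukemia or another cause, and are symptom-free, untreated and judged insignificant. Such an event is a DLT under the protocol and can be missing from the DLT count and the BLRM. The bias is toward fewer DLTs.

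Its size is not known. The documents give no frequency, and the detection table rests on assumed shares. The 0.47 to 0.14 shift at 4 subjects shows how much one event can weigh in a small cohort; it does not describe this trial's model.

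A reader might infer that a dose the model should block would be allowed. The documents do not support that. At 6 subjects the uniform prior gives 0.58 and 0.27, both above 0.25. The BLRM pools information across dose levels with a prior that is not fully shown, and the DLRT may go below its recommendation.

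The case for acting rests on the role of the DLT count in a first-in-human trial and on the small cost of the repair.

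**What to change.** **Protocol 9.2.2.1.** Add that any laboratory abnormality meeting a 6.2.1.3 DLT criterion, or not yet shown to be exempt from one, is entered on the Events eCRF whatever its judged clinical significance. The entry gives the onset date and the date of falling to the exempting grade, and the DLT question is answered. This is narrower than entering every grade 3 or higher value, which would also bring values already shown to be exempt into the adverse event tables.

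**SAP 5 and 9.6.1.** Add that before each BLRM run, grade 3-4 electrolyte and enzyme values in the DLT window, from laboratory data already collected, are listed against the DLT flags. Each mismatch is queried with the investigator, who keeps the attribution decision.

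**Limits.** The listing is a check and cannot replace the flag. GGT is in neither Protocol Table 15 nor the SAP 9.6.3 list, so it is covered only where sites measure it. In the two-dose Schedule A table (Protocol Table 6) the visit columns go from day 8 to day 14, so scheduled samples in that gap cannot establish a 72-hour limit. Attribution and absence of symptoms need the investigator.

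**Cost.** One protocol sentence, one SAP listing and some queries. No new samples are needed, and no DLT criterion, dose or clinical rule changes.
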